7. PHARMACY AND VACCINE ADMINISTRATION PROCEDURES

The study groups and study agent dosing schedule are shown in **Table 2** in **Section 4**. Refer to the IB for further information about the investigational study products.

7.1 STUDY PRODUCT

The study includes two investigational vaccines described as follows:

- VRC-FLUNPF081-00-VP at 180 mcg/mL. Vials contain 0.7 mL of a clear, colorless, isotonic buffered (pH=7.2) sterile solution. The formulation buffer consists of 20mM Sodium Phosphate, 100mM Sodium Chloride and 5% Sucrose. Vials are intended for single use only and do not contain a preservative.
- VRC-FLUDNA082-00-VP at 4 mg/mL. DNA A/Sing vaccine is supplied as a 3 mL glass vial containing a clear, colorless, isotonic, PBS-buffered (pH=7.2), sterile solution. Vials are intended for single use only and do not contain a preservative. Each vial (4 mg/mL) contains a volume of 1.2 mL (4.8 mg).

- VRC-PBSPLA043-00-VP (PBS), diluent, is a clear, colorless, sterile solution at pH 7.2, aseptically filled to a volume of 1.2 mL in a 3 mL glass vial. Vials are intended for single use only and do not contain preservative. Vials must not be refrozen or reused after thawing.

7.2 STUDY PRODUCT PRESENTATION AND STORAGE

7.2.1 Study Product Labels

VRC-FLUNPF081-00-VP and VRC-FLUDNA082-00-VP will have specific product information (e.g., part number, lot number, fill volume, storage temperature) included on the product vial labels. The label will contain an Investigational Use Statement (“Limited by Federal Law to Investigational Use”), and manufacturer information.

7.2.2 Study Product Storage

VRC-FLUNPF081-00-VP and VRC-FLUDNA082-00-VP vials will be shipped within the recommended temperature range using appropriate shipping configurations, to the study pharmacist or designee.

VRC-FLUNPF081-00-VP (HA-F A/Sing): Vials of vaccine are stored until use at -35°C to -15°C in a qualified, continuously monitored, temperature-controlled freezer. As freezer temperatures may fluctuate, a temperature range of -45°C to -15°C is acceptable.

VRC-FLUDNA082-00-VP (DNA A/Sing): Vials of vaccine are stored until use at -35°C to -15°C in a qualified, continuously monitored, temperature-controlled freezer. As freezer temperatures may fluctuate, a temperature range of -45°C to -10°C is acceptable. Storage below -45°C is not permitted because of the stopper limitation.

VRC-PBSPLA043-00-VP (PBS): Vials of PBS are stored until use at the target temperature of -35°C to -15°C in a qualified, continuously monitored, temperature-controlled freezer. As freezer temperatures may fluctuate, a temperature range of -45°C to -10°C is acceptable based upon historic stability data from studies of similar products.

7.2.3 Temperature excursions

If deviations in storage temperature occur from the normal allowance for the pharmacy freezer, the site pharmacist or designee must report the storage temperature excursion promptly to the PI and IND Sponsor. The excursion must be evaluated and investigated and action must be taken to restore and maintain the desired temperature limits. Pending the outcome of the investigation, the IND Sponsor will notify the pharmacist if continued clinical use of the product is acceptable.

7.3 PREPARATION OF STUDY PRODUCTS FOR INJECTION

This section describes how the site pharmacist will prepare study injections. Clinician instructions on how to select an arm and administer an injection are in Section 4.2.4. Refer to the group assignment for the study subject to select the proper vial type.

For all study groups, the prepared syringe will be labeled with the subject identifier and the date and time after which the preparation may not be used. Allow the vial to equilibrate to room temperature (15 to 30° C). Swirl the contents gently. Filled syringes should be kept at room temperature and out of direct sunlight until the product is administered. All injections must be administered within 8 hours after removing the vaccine vial from the freezer.

7.3.1 Preparation of VRC-FLUNPF081-00-VP to be administered via Needle and Syringe Injection

Subjects will receive the VRC-FLUNPF081-00-VP vaccine via needle and syringe injection. The following instructions apply for VRC-FLUNPF081-00-VP vaccine preparation:

Group 1 (20 mcg):

1. Thaw 1 vial of HA-F A/Sing at room temperature until all ice crystals have melted. Swirl gently to mix.
2. Thaw 1 vial of PBS diluent at room temperature until all ice crystals have melted. Swirl gently to mix.
3. Withdraw 0.11 mL of HA-F A/Sing into the syringe.
4. Withdraw 0.2 mL of PBS diluent directly into the syringe.
5. Invert syringe 5x to mix.

Group 2 and Groups 4A/B (60 mcg, prime and boost); Groups 3A/B (60 mcg, ONLY boost):

1. Thaw 1 vial of HA-F A/Sing at room temperature until all ice crystals have melted. Swirl gently to mix.
2. Withdraw 0.33 mL of HA-F A/Sing into the syringe.

Please refer to the IB for more information on vaccine preparation for injection.

7.3.2 Preparation of VRC-FLUDNA082-00-VP to be administered via PharmaJet Injection

For subjects randomized to **Group 3A/B** (PharmaJet), remove a single dose vial of the DNA vaccine 4 mg/mL from the freezer. Using aseptic technique, withdraw 0.5 mL of the DNA vaccine from the vial into the PharmaJet 0.5 mL needle-free syringe and remove all air bubbles. Two 0.5 mL injections of the 4 mg/mL preparation will be administered for each 4mg dose with the PharmaJet.

7.4 STUDY PRODUCT ACCOUNTABILITY

7.4.1 Documentation

The study pharmacist or designee will be responsible for maintaining an accurate record of the codes, inventory, and an accountability record of vaccine supplies for this study. Electronic documentation as well as paper copies will be used.

7.4.2 Disposition

The empty vials and the unused portion of a vial will be discarded in a biohazard containment bag and incinerated or autoclaved following the injection. Any unopened vials that remain at the end of the study will be discarded at the discretion of the VRC in accordance with policies that apply to investigational products. Partially used vials or expired prepared doses cannot be administered to other subjects nor used for *in vitro* experimental studies and will be discarded as indicated above.

8. HUMAN SUBJECT PROTECTIONS AND ETHICAL OBLIGATIONS

This research study will be conducted in compliance with the protocol, International Council for Harmonisation Good Clinical Practices (ICH-GCP) guidance, and all applicable regulatory requirements.

8.1 INSTITUTIONAL REVIEW BOARD

A copy of the protocol, ICF, other written subject information, and any advertising material will be submitted to the NIAID IRB for written approval prior to use.

The PI must submit and, where necessary, obtain approval from the IRB for all subsequent protocol amendments and changes to the ICF. The PI will notify the IRB of unanticipated problems, non-compliance, deviations from the protocol, and serious SAEs as described in Section 5.4.

The investigator will be responsible for obtaining IRB approval of the annual Continuing Review throughout the duration of the study.

8.2 SUBJECT IDENTIFICATION AND ENROLLMENT OF STUDY PARTICIPANTS

Study subjects will be recruited through on-site and off-site advertising done for the screening protocol, VRC 500 (11-I-0164). All study activities will be carried out at the NIH CC. Effort will be made to include women and minorities in proportions similar to that of the community from which they are recruited.

8.2.1 Participation of Children

Children are not eligible to participate in this clinical trial because the investigational vaccine regimens have not been previously evaluated in adults. If the product is assessed as safe and immunogenic, other protocols designed for children may be conducted in the future.

8.2.2 Participation of NIH Employees

NIH employees and members of their immediate families may participate in this protocol. NIH staff may be a vulnerable class of subjects. The VRC will follow the Guidelines for the Inclusion of Employees in NIH Research Studies and will give each employee a copy of the “NIH Information Sheet on Employee Research Participation” and a copy of the “Leave Policy for NIH Employees Participating in NIH Medical Research studies.”

Neither participation nor refusal to participate will have an effect, either beneficial or adverse, on the participant’s employment or work situation. The NIH information sheet regarding NIH employee research participation will be distributed to all potential subjects who are NIH employees. The employee subject’s privacy and confidentiality will be preserved in accordance with NIH CC and NIAID policies. For NIH employee subjects, consent will be obtained by an individual who is independent of the employee’s team. If the individual obtaining consent is a co-worker to the subject, independent monitoring of the consent process will be included through the Bioethics Consultation Service. Protocol study staff will be trained on obtaining potentially sensitive and private information from co-workers or subordinates.

8.3 INFORMED CONSENT

The study ICF, , describes the investigational products to be used and all aspects involved in protocol participation.

Before a subject’s participation in the study, it is the investigator’s responsibility to obtain written informed consent from the subject, after adequate explanation of the aims, methods, anticipated benefits, and potential hazards of the study and before any protocol-specific procedures or study products are administered.

An IRB-approved AoU quiz, intended to assist in the evaluation of the subject's understanding of this study, is administered as part of the consent process.

The acquisition of informed consent will be documented in the subject's medical records, as required by 21 CFR 312.62, and the ICF will be signed and personally dated by the subject and by the person who conducted the informed consent discussion. The original signed ICF will be placed in the medical record and a copy of the signed ICF will be provided to the subject.

8.4 SUBJECT CONFIDENTIALITY

The investigator must ensure that the subject's anonymity is maintained and will ensure that no information identifying the subject will be released to any unauthorized party. Subjects will not be identified in any reports on this study. All records will be kept confidential to the extent provided by federal, state and local law. Medical records are made available for review when required by the FDA or other authorized users, such as the vaccine manufacturer, only under the guidelines set by the Federal Privacy Act. Direct access includes examining, analyzing, verifying, and reproducing any records and reports that are important to the evaluation of the study. The investigator is obligated to inform the subjects that the above-named representatives will review their study-related records without violating the confidentiality of the subjects. Stored study research samples are labeled by a code (such as a number) that only the study team can link to the subject. The requirement to maintain subject confidentiality is included in the study ICF.

8.5 RISKS AND BENEFITS

8.5.1 Risks of the VRC-FLUNPF081-00-VP vaccine

This is the first study in humans of this investigational VRC-FLUNPF081-00-VP vaccine. This product is derived from *H. pylori* ferritin and not human ferritin, for this reason it is not expected to interfere with iron storage, transport or iron serum levels [13].

Potential side effects resulting from IM injection include stinging, arm discomfort, redness of the skin or mild bruising at vaccine injection sites.

Subjects may exhibit general signs and symptoms associated with administration of a vaccine, including fever, chills, rash, aches and pains, nausea, headache, dizziness and fatigue. These side effects will be monitored, but are generally short term, mild to moderate severity and usually do not require treatment.

There may be other unknown side effects.

8.5.2 Risks of the VRC-FLUDNA082-00-VP Vaccine

This is the first study in humans of the investigational DNA vaccine, VRC-FLUDNA082-00-VP. The risks noted are based on risks of vaccines in general, and results of previous studies with other investigational DNA vaccines.

Potential side effects resulting from IM injection with PharmaJet include stinging, arm discomfort, redness of the skin, mild bruising or a small laceration at vaccine injection sites.

There is also a small chance that the needle-free device could not work properly. As of June 26, 2017, there have been 8 out of 426 (1.9%) injections that involved device malfunction in VRC 705 Part A. This includes the syringe breaking and study product spraying during administration. No harm to subjects has occurred when this happened. Investigations are ongoing

to determine the factors leading to malfunction. As a result, Subjects in Group 3A/B and clinicians administering the vaccine will be asked to wear safety glasses when using PharmaJet.

Subjects may exhibit general signs and symptoms associated with administration of a vaccine injection, including fever, chills, rash, aches and pains, nausea, headache, dizziness and fatigue.

These side effects will be monitored, but are generally short-term, mild to moderate severity and usually do not require treatment.

In previous VRC DNA vaccine studies, placebo and vaccine recipients were noted to have occasional asymptomatic and self-limited changes in laboratory tests such as temporary drop in white blood cell count. Urticaria has been reported as possibly related to DNA vaccines in rare cases.

Investigational DNA vaccines administered via needleless injection device have been associated with mild skin lesions (0.5-1.0 cm diameter) at the vaccination site. In these cases a small scab formed within 1-2 weeks after immunization and came off after a few days. The skin healed without treatment within a few weeks. We do not know if the side effects from PharmaJet will be the same as Biojector. There may be other unknown side effects.

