Subjects will be given a “Diary Card” to use as a memory aid, on which to record temperature and symptoms daily for 7 days after each injection. Subjects will be trained and encouraged to use the secure electronic database but will have the option to complete a paper diary card. When the diary card parameters are recorded directly by the subject in the electronic database, the subject’s electronic record will be the source for these data. When collected on paper, the paper diary card will be used as a source document. When neither paper nor electronic diary is available from the subject, the study clinician will document the source of reactogenicity information recorded in the study database.

The solicited signs and symptoms on the diary card will include the following parameters: unusually tired/feeling unwell, muscles aches (other than at injection site), headache, chills, nausea, joint pain, and pain/tenderness at injection site. Subjects will also record the day’s highest measured temperature and measurement of largest diameter for redness and swelling at injection site.

Follow-up on subject well-being will be performed by telephone on the first day following all injections and by clinic visits as shown in the Schedule of Evaluations (Appendix II)

Events following any study injection that may require clinical evaluation include rash, urticaria, fever of 38.5°C (Grade 2) or higher lasting greater than 24 hours, or significant impairment in the activities of daily living. Additionally, other clinical concerns may prompt a study visit based on the judgment of a study clinician.

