6.3 ENDPOINTS

6.3.1 Primary Endpoints: Safety

Assessment of product safety will include clinical observation and monitoring of hematological and chemical parameters. Reactogenicity will be closely monitored for 7 days after each injection and safety evaluated by clinical visits throughout 40 weeks. See Section 4.2 and Appendix II for details and specified time points.

The following parameters will be assessed for all study groups:

- Occurrence of solicited local reactogenicity symptoms for 7 days following each injection
- Occurrence of solicited systemic reactogenicity symptoms for 7 days following each injection
- Change from baseline in safety laboratory measures
- Occurrence of AEs of all severities through the “Week 4” visit after each injection
- Occurrence at any time throughout the study of SAEs or new chronic medical conditions that require ongoing medical management.

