 Modified from FDA Guidance - September 2007**

A. Tables for Clinical Abnormalities

Local Reaction to Injectable Product	Mild (Grade 1)	Moderate (Grade 2)	Severe (Grade 3)	Potentially Life Threatening (Grade 4)
Pain	Does not interfere with activity	Repeated use of non-narcotic pain reliever > 24 hours or interferes with activity	Any use of narcotic pain reliever or prevents daily activity	Hospitalization
Tenderness	Mild discomfort to touch	Discomfort with movement	Significant discomfort at rest	Hospitalization
¹ Erythema/Redness	2.5 – 5 cm	5.1 – 10 cm	> 10 cm	Necrosis or exfoliative dermatitis requiring medical attention
² Induration/Swelling	2.5 – 5 cm and does not interfere with activity	5.1 – 10 cm or interferes with activity	> 10 cm or prevents daily activity	Necrosis requiring medical attention
³Vital Signs	Mild (Grade 1)	Moderate (Grade 2)	Severe (Grade 3)	Potentially Life Threatening (Grade 4)
⁴ Fever (°C) (°F)	38.0 – 38.4 100.4 – 101.1	38.5 – 38.9 101.2 – 102.0	39.0 – 40 102.1 – 104	> 40 > 104
Tachycardia - beats per minute	101 – 115	116 – 130	> 130	Hospitalization for arrhythmia

⁵ Bradycardia - beats per Minute	50 – 54	45 – 49	< 45	Hospitalization for arrhythmia
Hypertension (systolic) - mm Hg	141 – 150	151 – 155	> 155	Hospitalization for malignant hypertension
Hypertension (diastolic) - mm Hg	91 – 95	96 – 100	> 100	Hospitalization for malignant hypertension
Hypotension (systolic) – mm Hg	85 – 89	80 – 84	< 80	Hospitalization for hypotensive shock
Respiratory Rate – breaths per minute	17 – 20	21 – 25	> 25	Intubation

1. In addition to grading the measured local reaction at the greatest single diameter, the measurement should be recorded as a continuous variable.
2. Induration/Swelling should be evaluated and graded using the functional scale as well as the actual measurement.
3. Subject should be at rest for all vital sign measurements.
4. Oral temperature; no recent hot or cold beverages or smoking.
5. When resting heart rate is between 60 – 100 beats per minute. Use clinical judgment when characterizing Bradycardia among some healthy subject populations, for example, conditioned athletes.

Systemic (General)	Mild (Grade 1)	Moderate (Grade 2)	Severe (Grade 3)	Potentially Life Threatening (Grade 4)
Nausea/vomiting	No interference with activity or 1 – 2 episodes/24 hours	Some interference with activity or > 2 episodes/24 hours	Prevents daily activity, requires outpatient IV hydration	Hospitalization for hypotensive shock

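### The graded 7-day local-reactogenicity table is insensitive to the small skin lesions described for needle-free DNA injection, and the AE route that can record them is passive

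*Combined protocol and SAP*

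**What the plan says.** Section 3.1 makes the safety and tolerability of the DNA vaccine by needle-free device a primary objective. Only Group 3 receives it, as two 0.5 mL PharmaJet injections on Day 0 (Sections 4.2.4 and 7.3.2).

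Section 8.5.2 reports that DNA vaccines given by needle-free device were "associated with mild skin lesions (0.5-1.0 cm diameter) at the vaccination site. In these cases a small scab formed within 1-2 weeks after immunization". The skin is said to have healed untreated within a few weeks. On whether this carries over to the device used here, the section states: "We do not know if the side effects from PharmaJet will be the same as Biojector". For PharmaJet itself it lists stinging, arm discomfort, redness, mild bruising and a small laceration.

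The local measurements are as follows.

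- **Diary (Section 4.2.5):** a card "on which to record temperature and symptoms daily for 7 days after each injection". Its local items are pain or tenderness and "measurement of largest diameter for redness and swelling at injection site".
- **Grading (Appendix III, table A):** Grade 1 swelling is "2.5 – 5 cm and does not interfere with activity". Redness has the same lower limit. The notes ask that the local-reaction diameter also be kept as a continuous value, and that swelling be graded by function as well as size.
- **Endpoint (Section 6.3.1):** one of five primary safety parameters is "Occurrence of solicited local reactogenicity symptoms for 7 days following each injection". Another is AEs of every severity up to the Week 4 visit after each injection.
- **Analysis:** solicited signs are tabulated by maximum severity (Section 6.5.3.1). AEs are tabulated by severity and relationship, and listed per participant (Section 6.5.3.2).
- **Examination:** the injection site is inspected after injection on the day (Section 4.2.4). At later visits a physical examination is done only if history or laboratory results call for one; otherwise blood pressure, pulse and temperature suffice (Appendix II, footnote 2).

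**The concern.** The solicited local table is where a reader will look for the local tolerability of the needle-free DNA injection. Its items, size floor and time window do not match the route-specific skin lesion that the protocol itself describes. If such lesions occur, the table will probably not show them. Their appearance elsewhere depends on a subject mentioning a small, mild scab or on a clinician happening to notice it.

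At stake is how a low count is read. The product is first-in-human, Section 2.5 says that no product-specific preclinical toxicology was done, and the device's local profile is stated to be unknown. This trial could inform that question, but an absence of reports is informative only if someone looked.

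**Working it through.** The plan gives no figure on this point, so the check sets thresholds and time windows side by side. One short calculation then shows what a zero count would mean. Visit days are read from the Appendix II headers and footnotes.

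**1. Items.** Described lesion: a skin lesion with a scab. Diary skin items: redness and swelling diameters. There is no entry for lesion, scab, bruise or laceration.

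**2. Size.** Described diameter 0.5-1.0 cm (Section 8.5.2); lowest size grade 2.5 cm (Appendix III).

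- 0.5 / 2.5 = 0.20 and 1.0 / 2.5 = 0.40
- 2.5 - 1.0 = 1.5 cm, the shortfall for the largest described lesion

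Redness or swelling confined to an area of that size would get no grade on diameter. Swelling can also be graded on interference with activity, but a lesion described as mild is unlikely to qualify that way. The continuous diameter is kept, yet Section 6.5.3.1 plans no summary of values below Grade 1.

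**3. Time.** The diary ends at Day 7. Section 8.5.2 says "a small scab formed within 1-2 weeks after immunization and came off after a few days". Forming within 1-2 weeks allows an earlier visible lesion, so the overlap with the diary is not zero, but much of the period (Day 7 to Day 14) lies after it. Section 5.1 provides for follow-up of symptoms unresolved at Day 7. That covers solicited symptoms already present, not a scab that first appears in week 2.

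**4. The other route.** Unsolicited AEs are recorded with attribution from first injection to the Week 4 visit (Section 5.1). Where no specific scale applies, Appendix III grades an event with no effect on daily activities as Grade 1, with no size limit. The recording period covers the whole scab range. Clinic visits fall at Day 6 ±1 (Visit 03), Day 14 ±2 (Visit 04) and Day 28 ±2 (Visit 05), each with interim history but no required look at the arm.

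**5. What a zero would mean.** The plan's nearest figure is the exact two-sided 95% upper bound for 0/10 in Table 6-2, 0.308. It is reproduced by 1 - 0.025^(1/10) = 0.308. For the 20 planned Group 3 subjects (3A + 3B), 1 - 0.025^(1/20) = 0.168. That bound applies to the rate of *recorded* lesions.

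Let p be the true per-subject lesion rate and s the probability that a lesion is recorded as an AE. Neither is in the documents, so the values below are assumptions. Then P(none recorded in 20) = (1 - ps)^20:

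| s | p = 0.10 | p = 0.30 |
|---|---|---|
| 0 (graded solicited table alone, assuming it catches none) | 1.00 | 1.00 |
| 0.25 | 0.975^20 = 0.60 | 0.925^20 = 0.21 |
| 0.5 | 0.95^20 = 0.36 | 0.85^20 = 0.04 |
| 1 | 0.90^20 = 0.12 | 0.70^20 = 0.001 |

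Equivalently, 0/20 recorded bounds ps at 0.168, so the bound on p is 0.168 / s: 0.168 at s = 1, about 0.34 at s = 0.5 and about 0.67 at s = 0.25. Because s is unknown under passive capture, no useful bound on p follows from a zero.

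**The case against.** The strongest reply is that solicited local signs are only one of five parallel primary safety parameters. A 0.5 cm scab on Day 10 is recordable as a Grade 1 AE inside the primary endpoint, with attribution, tabulation and a listing. This stands. A reader might infer that the endpoint cannot register the lesion, or that the DNA arm would look free of it by construction. The documents do not support that: in the table above a zero is certain only when the AE component is ignored.

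Other points that stand, in whole or in part:

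- A reader might take Section 8.5.2 to predict this lesion for PharmaJet. It reports an association with needle-free devices and calls the carry-over unknown. That weakens any claim about how often it will occur, but it is also a reason to look.
- The 2.5 cm floor belongs to redness and swelling, not scabs, so the 20-40% ratio compares different signs. It shows only that the existing size scale offers no entry point.
- Clinicians take interim history at about Days 6, 14 and 28, and rash is named in Section 4.2.5 as an event that may require evaluation. Capture is therefore not purely a matter of volunteering. Still, none of this requires the site to be looked at.
- The case report form is not among the documents and may hold an injection-site field. If so, the protocol should say so.
- The lesions are mild and healed untreated, the analysis is descriptive, and a mild lesion of this kind would not meet the pause criteria in Section 4.5.1. The point concerns completeness of measurement; nothing here suggests that subjects are endangered.
- Closer inspection of Group 3 alone would make ascertainment unequal in an open-label randomized comparison, and mild bruising is also listed for the ferritin vaccine (Section 8.5.1). This is right, and the fix below covers both groups.

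**Conclusion.** The point holds as a limit on ascertainment, of modest weight. The graded solicited local table is insensitive to the lesion on items, size (at most 1.0 cm against 2.5 cm) and, for much of the scab period, time. The AE component of the primary endpoint can capture it at any size up to Week 4, but only passively, so a zero or low count would not reliably show absence. Even with complete capture, 0/20 leaves a 95% upper bound of 0.168; with incomplete capture the bound on the true rate is wider by an unknown factor.

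This rests on the planned 20 Group 3 subjects, on reading Appendix II footnote 2 as requiring no routine site check after the injection day, and on the case report form containing no such check. The capture probabilities are illustrative.

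**What to change.** At the existing Visits 03, 04 and 05, inspect the prime injection site or sites in both Group 3 and Group 4. Record presence and diameter of any lesion, scab, bruise or laceration, whatever its size. In Section 6.5.3.1, add a per-subject tabulation of these findings by group beside the solicited local table, together with a summary of redness and swelling diameters below 2.5 cm. State whether each finding is also entered as an AE, so that it is not counted twice.

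The cost is one case report form item, a brief look at the arm at visits already planned, a few table rows, and more minor findings listed. No visit or sample is added. Inspection will not be perfect: with the visit windows, Visit 03 falls no later than Day 7 and Visit 04 no earlier than Day 12, so a short-lived scab between them may show only as a healing mark. It would nonetheless make a zero count mean that the sites were examined on defined days.
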